7.6 USE OF COMPUTERIZED SYSTEMS

When clinical observations are entered directly into a study site's computerized medical record system (i.e., in lieu of original hardcopy records), the electronic record can serve as the source document if the system has been validated in accordance with HA requirements pertaining to computerized systems used in clinical research. An acceptable computerized data collection system allows preservation of the original entry of data. If original data are modified, the system should maintain a viewable audit

trail that shows the original data as well as the reason for the change, name of the person making the change, and date of the change.

7.7 RETENTION OF RECORDS

Records and documents pertaining to the conduct of this study and the distribution of IMP, including eCRFs, electronic or paper PRO, PerfO, and ClinRO data (if applicable), ICFs, laboratory test results, and medication inventory records, must be retained by the Principal Investigator for 15 years after completion or discontinuation of the study or for the length of time required by relevant national or local HAs, whichever is longer. After that period of time, the documents may be destroyed, subject to local regulations.

No records may be disposed of without the written approval of the Sponsor. Written notification should be provided to the Sponsor prior to transferring any records to another party or moving them to another location.

Roche will retain study data for 25 years after the final Clinical Study Report has been completed or for the length of time required by relevant national or local HAs, whichever is longer.

8. ETHICAL CONSIDERATIONS

8.1 COMPLIANCE WITH LAWS AND REGULATIONS

This study will be conducted in full conformance with the ICH E6 guideline for Good Clinical Practice and the principles of the Declaration of Helsinki, or the applicable laws and regulations of the country in which the research is conducted, whichever affords the greater protection to the individual. The study will comply with the requirements of the ICH E2A guideline (Clinical Safety Data Management: Definitions and Standards for Expedited Reporting). Studies conducted in the U.S. or under a U.S. Investigational New Drug (IND) Application will comply with U.S. FDA regulations and applicable local, state, and federal laws. Studies conducted in the European Union (E.U.) or European Economic Area will comply with the E.U. Clinical Trial Directive (2001/20/EC) and applicable local, regional, and national laws.

8.2 INFORMED CONSENT

The Sponsor's sample ICF (and ancillary sample ICFs) will be provided to each site. If applicable, it will be provided in a certified translation of the local language. The Sponsor or its designee must review and approve any proposed deviations from the Sponsor's sample ICFs or any alternate consent forms proposed by the site (collectively, the "Consent Forms") before IRB/EC submission. The final IRB/EC-approved Consent Forms must be provided to the Sponsor for HA submission purposes according to local requirements.

If applicable, the ICF will contain separate sections for any optional procedures. The investigator or authorized designee will explain to each patient the objectives, methods,

and potential risks associated with each optional procedure. Patients will be told that they are free to refuse to participate and may withdraw their consent at any time for any reason. A separate, specific signature will be required to document a patient's agreement to participate in optional procedures. Patients who decline to participate will not provide a separate signature.

The Consent Forms must be signed and dated by the patient or the patient's legally authorized representative before his or her participation in the study. The case history or clinical records for each patient shall document the informed consent process and that written informed consent was obtained prior to participation in the study. If the legally authorized representative signs the Consent Form with the patient, the patient will still need to provide assent in the case he/she is no longer capable of providing consent. Assent implies willingness or, minimally, lack of objection to taking part and will need to be documented by the site. (Note: Patients in Germany who are not fully capable of providing informed consent are not eligible for participation).

The Consent Forms should be revised whenever there are changes to study procedures or when new information becomes available that may affect the willingness of the patient to participate. The final revised IRB/EC-approved Consent Forms must be provided to the Sponsor for HA submission purposes.

Patients must be re-consented to the most current version of the Consent Forms (or to a significant new information/findings addendum in accordance with applicable laws and IRB/EC policy) during their participation in the study. For any updated or revised Consent Forms, the case history or clinical records for each patient shall document the informed consent process and that written informed consent was obtained using the updated/revised Consent Forms for continued participation in the study. If the legally authorized representative signs the Consent Form for the patient, the patient will still need to provide assent in the case that he/she is no longer fully capable of providing consent. (Note: Patients in Germany who are not fully capable of providing informed consent are not eligible for participation).

A copy of each signed Consent Form must be provided to the patient or the patient's legally authorized representative. All signed and dated Consent Forms must remain in each patient's study file or in the site file and must be available for verification by study monitors at any time.

For sites in the U.S., each Consent Form may also include patient authorization to allow use and disclosure of personal health information in compliance with the U.S. Health Insurance Portability and Accountability Act (HIPAA) of 1996. If the site utilizes a separate Authorization Form for patient authorization for use and disclosure of personal health information under the HIPAA regulations, the review, approval, and other processes outlined above apply except that IRB review and approval may not be required per study site policies.

8.3 INSTITUTIONAL REVIEW BOARD OR ETHICS COMMITTEE

This protocol, the ICFs, any information to be given to the patient, and relevant supporting information must be submitted to the IRB/EC by the Principal Investigator and reviewed and approved by the IRB/EC before the study is initiated. In addition, any patient recruitment materials must be approved by the IRB/EC.

The Principal Investigator is responsible for providing written summaries of the status of the study to the IRB/EC annually or more frequently in accordance with the requirements, policies, and procedures established by the IRB/EC. Investigators are also responsible for promptly informing the IRB/EC of any protocol amendments (see Section 9.7).

In addition to the requirements for reporting all AEs to the Sponsor, investigators must comply with requirements for reporting SAEs to the local HA and IRB/EC. Investigators may receive written IND safety reports or other safety-related communications from the Sponsor. Investigators are responsible for ensuring that such reports are reviewed and processed in accordance with HA requirements and the policies and procedures established by their IRB/EC, and archived in the site's study file.

8.4 CONFIDENTIALITY

The Sponsor maintains confidentiality standards by coding each patient enrolled in the study through assignment of a unique patient identification number. This means that patient names are not included in data sets that are transmitted to any Sponsor location.

Patient medical information obtained by this study is confidential and may be disclosed to third parties only as permitted by the ICF (or separate authorization for use and disclosure of personal health information) signed by the patient, unless permitted or required by law.

Medical information may be given to a patient's personal physician or other appropriate medical personnel responsible for the patient's welfare, for treatment purposes.

Given the complexity and exploratory nature of exploratory biomarker analyses, data derived from these analyses will generally not be provided to study investigators or patients unless required by law. The aggregate results of any conducted research will be available in accordance with the effective Sponsor policy in the study data publication (see Section 9.6).

Data generated by this study must be available for inspection upon request by representatives of national and local HAs, Sponsor monitors, representatives, and collaborators, and the IRB/EC for each study site, as appropriate.

Study data may be submitted to government or other health research databases or shared with researchers, government agencies, companies, or other groups that are not participating in this study. These data may be combined with or linked to other data and

used for research purposes, to advance science and public health, or for analysis, development, and commercialization of products to treat and diagnose disease. Linking of data will be facilitated by the HDID number (see Section 4.5.2). The HDID is a unique coded identifier for persons participating in studies in HD. This HDID will stay the same for a person throughout all trials. The use of the unique identifier will assure that people are only enrolled once in large observational studies like ENROLL-HD, REGISTRY, COHORT, PREDICT-HD, and TRACK-HD and will also allow approved comparison and combination of data between studies. The HDID is a 9-digit number created by a secure one-way algorithm, based on unchanging information (date of birth, birth name, place of birth, and mother's maiden name). The identifying data are used for the split second needed by the algorithm needed to generate the HDID and are never stored electronically on the web portal or in the study database. It is expected that patients from preceding studies have a pre-existing HDID number. For patients without a pre-existing HDID number in the source notes, the investigator should store the original data and the newly generated HDID in the patient's source documents and in the investigator file. The HDID can be generated within the web portals of the observational studies or in the specially defined portal for the HDID generation under:

<https://hdid.enroll-hd.org>.

In addition, redacted Clinical Study Reports and other summary reports will be provided upon request.

8.5 FINANCIAL DISCLOSURE

Investigators will provide the Sponsor with sufficient, accurate financial information in accordance with local regulations to allow the Sponsor to submit complete and accurate financial certification or disclosure statements to the appropriate HAs. Investigators are responsible for providing information on financial interests during the course of the study and for 1 year after completion of the study (see definition of end of study in Section 3.2).

9. STUDY DOCUMENTATION, MONITORING, AND ADMINISTRATION

9.1 STUDY DOCUMENTATION

The investigator must maintain adequate and accurate records to enable the conduct of the study to be fully documented, including, but not limited to, the protocol, protocol amendments, ICFs, and documentation of IRB/EC and governmental approval. In addition, at the end of the study, the investigator will receive the patient data, including an audit trail containing a complete record of all changes to data.

9.2 PROTOCOL DEVIATIONS

The investigator should document and explain any protocol deviations. The investigator should promptly report any deviations that might have an impact on patient safety and data integrity to the Sponsor and to the IRB/EC in accordance with established IRB/EC policies and procedures. The Sponsor will review all protocol deviations and assess

whether any represent a serious breach of Good Clinical Practice guidelines and require reporting to HAs. As per the Sponsor's standard operating procedures, prospective requests to deviate from the protocol, including requests to waive protocol eligibility criteria, are not allowed.

9.3 MANAGEMENT OF STUDY QUALITY

The Sponsor will implement a system to manage the quality of the study, focusing on processes and data that are essential to ensuring patient safety and data integrity. The Sponsor will identify potential risks associated with critical trial processes and data and will implement plans for evaluating and controlling these risks. Risk evaluation and control will include the selection of risk-based parameters (e.g., AE rate, protocol deviation rate) and the establishment of quality tolerance limits for these parameters. Detection of deviations from quality tolerance limits will trigger an evaluation to determine if action is needed. Details on the establishment and monitoring of quality tolerance limits will be provided in a Quality Tolerance Limit Management Plan.

9.4 SITE INSPECTIONS

Site visits will be conducted by the Sponsor or an authorized representative for inspection of study data, patients' medical records, and eCRFs. The investigator will permit national and local HAs; Sponsor monitors, representatives, and collaborators; and the IRBs/ECs to inspect facilities and records relevant to this study.

9.5 ADMINISTRATIVE STRUCTURE

This trial will be sponsored and managed by F. Hoffmann-La Roche Ltd. The Sponsor will provide clinical operations management, data management, and medical monitoring.

Approximately 100 sites globally will participate to enroll up to approximately 1100 patients. Enrollment will occur through an IxRS.

Central facilities will be used for certain study assessments throughout the study (e.g., specified laboratory tests, biomarker and PK analyses), as specified in Section 4.5.6. Accredited local laboratories will be used for routine monitoring; local laboratory ranges will be collected.

9.6 DISSEMINATION OF DATA AND PROTECTION OF TRADE SECRETS

Regardless of the outcome of a trial, the Sponsor is dedicated to openly providing information on the trial to healthcare professionals and to the public, at scientific congresses, in clinical trial registries, and in peer-reviewed journals. The Sponsor will comply with all requirements for publication of study results. Study data may be shared with others who are not participating in this study (see Section 8.4 for details) and redacted Clinical Study Reports and other summary reports will be made available upon request, provided the requirements of Roche's global policy on data sharing have been met. For more information, refer to the Roche Global Policy on Sharing of Clinical Trials Data at the following website:

www.roche.com/roche_global_policy_on_sharing_of_clinical_study_information.pdf

The results of this study may be published or presented at scientific congresses. For all clinical trials in patients involving an IMP for which a Marketing Authorization Application has been filed or approved in any country, the Sponsor aims to submit a journal manuscript reporting primary clinical trial results within 6 months after the availability of the respective Clinical Study Report. In addition, for all clinical trials in patients involving an IMP for which a Marketing Authorization Application has been filed or approved in any country, the Sponsor aims to publish results from analyses of additional endpoints and exploratory data that are clinically meaningful and statistically sound.

The investigator must agree to submit all manuscripts or abstracts to the Sponsor prior to submission for publication or presentation. This allows the Sponsor to protect proprietary information and to provide comments based on information from other studies that may not yet be available to the investigator.

In accordance with standard editorial and ethical practice, the Sponsor will generally support publication of multicenter trials only in their entirety and not as individual center data. In this case, a coordinating investigator will be designated by mutual agreement.

Authorship will be determined by mutual agreement and in line with International Committee of Medical Journal Editors authorship requirements. Any formal publication of the study in which contribution of Sponsor personnel exceeded that of conventional monitoring will be considered as a joint publication by the investigator and the appropriate Sponsor personnel.

Any inventions and resulting patents, improvements, and/or know-how originating from the use of data from this study will become and remain the exclusive and unburdened property of the Sponsor, except where agreed otherwise.

9.7 PROTOCOL AMENDMENTS

Any protocol amendments will be prepared by the Sponsor. Protocol amendments will be submitted to the IRB/EC and to regulatory authorities in accordance with local regulatory requirements.

Approval must be obtained from the IRB/EC and regulatory authorities (as locally required) before implementation of any changes, except for changes necessary to eliminate an immediate hazard to patients or changes that involve logistical or administrative aspects only (e.g., change in Medical Monitor or contact information).

Appendix 1a Schedule of Activities for All Patients Except Those Undergoing Screening

	Inclusion Visit ^a	Treatment Period ^b	EoT ^c	SFU ^d
Week	Last applicable visit of preceding study ^a	Treatment and Assessment Frequency	+4 weeks	+20 weeks
Day (Window)		±1 week ^e	±1 week	±1 week
Signed informed consent ^f	x			
Review of inclusion and exclusion criteria	x			
Demographic data	x			
Medical history and baseline conditions ^g	x			
Vital signs ^h	x ⁱ	At each clinic visit	x	x
Complete physical examination ^j	x ⁱ	Q32W	x	x
Neurologic examination ^l	x ⁱ	At each clinic visit (see Appendix 12)	x	x
ECG ^m	x ⁱ	Q32W	x	x
Hematology ⁿ	x ⁱ	At each clinic visit	x	x
Chemistry ^o	x ⁱ		x	x
Pregnancy test ^p	x ⁱ		x	x
Urinalysis ^q	x ⁱ		x	x
Local PT and/or INR, aPTT, platelet count ^s	x ⁱ	At each study drug administration visit	x	x

Appendix 1a
Schedule of Activities for All Patients Except Those Undergoing Screening (cont.)

	Inclusion Visit ^a	Treatment Period ^b	EoT ^c	SFU ^d
Week	Last applicable visit of preceding study ^a	Treatment and Assessment Frequency	+4 weeks	+20 weeks
Day (Window)		±1 week ^e	±1 week	±1 week
Plasma sampling for PK ^r	x ⁱ	Q16W for 48 weeks and then Q32W thereafter		
Plasma sampling for immunogenicity testing ^r	x ⁱ		x	x
Plasma samples for biomarkers	x ⁱ		x	x
CSF sample for PK/safety/biomarkers ^s	x ⁱ	At each study drug administration	x	
MoCA	x ⁱ	Q16W	x	
C-SSRS ^t	x ⁱ	At each study drug administration	x	
Mandatory Structural MRI ^u	x ⁱ	Q32W ^k	x	
Optional resting-state functional MRI and diffusion-weighted MRI / NODDI ^u	x ⁱ	Q32W ^k	x	
Optional MRI brain and spine with contrast media for patients from Study BN40697 ^v	x	Q32W	x	

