2.5 EXPLORATORY BIOMARKER OBJECTIVE

The exploratory biomarker objective for this study is to identify biomarkers that are early surrogates of efficacy, are associated with progression to a more severe disease state (i.e., prognostic biomarkers), are associated with acquired resistance to RO7234292, are associated with susceptibility to developing AEs or can lead to improved AE monitoring or investigation (i.e., safety biomarkers), can provide evidence of RO7234292 activity

(i.e., PD biomarkers), or can increase the knowledge and understanding of disease biology and drug safety, on the basis of the following endpoints:

- Relationship between biomarkers (e.g., tau and neurofilament light chain protein [NfL]) in plasma and CSF (listed in Section 4.5.6) and efficacy, safety, PK, immunogenicity, or other biomarker endpoints
- Relationship between imaging biomarkers and efficacy, safety, PK, immunogenicity, or other biomarker endpoints

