3.3.2.3 Magnetic Resonance Imaging

Magnetic resonance imaging is a non-invasive method to assess structure and function of the human brain and can provide insights into pathophysiological mechanisms of neurologic and neuropsychiatric disease. Several MRI techniques have shown sensitivity to detect abnormal structure and function within brains of individuals suffering from HD.

All patients will undergo MRIs every 32 weeks to assess the effect of long-term treatment and LP on brain structure and function. All of the measures will be assessed in a consistent manner with the preceding study, including those designated to be optional. The acquisition parameters of each sequence, structure, and length of each MRI session and image processing algorithms will be outlined in a separate MRI manual.

Unscheduled MRIs in 3 patients who received monthly IT procedures in Study BN40697 reported enhancement in the cauda equina region; MRIs will be explored in this extension study to further assess the impact of frequent IT procedures.

For this purpose, in consenting patients from Study BN40697, optional MRI scans of brain and spine with contrast media will be collected upon study entry and every 32 weeks thereafter (for additional details refer to Study BN40955 Ixco Safety Read Manual). The contrast brain and spine MRI will be reviewed in-house or by ad-hoc independent external neuroimaging experts to look for the occurrence of abnormal MRI findings.

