Appendix 1a

Schedule of Activities for All Patients Except Those Undergoing Screening (cont.)

CGI-C=Clinical Global Impression, Change; CGI-S=Clinical Global Impression, Severity; C-SSRS=Columbia-Suicide Severity Rating Scale; CSF=cerebrospinal fluid; cUHDRS=composite Unified Huntington's Disease Rating Scale; eCRF=electronic Case Report Form; EoT=end-of-treatment; EQ-5D-5L=EuroQol 5-Dimension, 5 Level Questionnaire; HD=Huntington's disease; HD-DAS=HD Daily Activities Scale; LP=lumbar puncture; MoCA=Montreal Cognitive Assessment; MRI=magnetic resonance imaging; NODDI=Neurite Orientation Dispersion and Density Imaging; PK=pharmacokinetic; SDMT=Symbol Digit Modalities Test; SFU=safety follow-up; SWR=Stroop Word Reading; TFC=Total Functional Capacity Scale; TMS=Total Motor Score; Q8W=every 8; Q16W=every 16 weeks; Q32W=every 32 weeks.

Notes: All assessments should be performed at the scheduled visit, unless otherwise specified. On treatment days, all assessments should be performed prior to dosing, unless otherwise specified.

- ^a Inclusion visit should be the last applicable visit of the preceding study as defined in Section 3.1.1. For patients entering from Study BN40423 prior to implementation of Protocol Version 4, the inclusion visit should occur at the end-of-treatment visit for Study BN40423. For patients entering from Study BN40697, in the event of any delay in start-up activities where it is not possible to conduct the inclusion visit at the time of the last applicable visit in Study BN40697, a separate inclusion visit should be scheduled 4 weeks or 8 weeks (± 1 week) for a patient previously treated Q4W or 8 weeks (± 1 week) later for a patient previously treated Q8W.
- ^b If dosing at the inclusion visit is not possible, the Medical Monitor should be consulted and a short treatment interruption may be permitted.
- ^c Patients who complete treatment (e.g., will continue treatment on commercially available drug) or who discontinue study drug prematurely will return to the clinic for a treatment completion visit 4 weeks (± 7 days) after the decision to discontinue. For patients continuing treatment with RO7234292 outside of the study, the end of study visit should occur before the patient's next dose of RO7234292.
- ^d Safety follow-up visit occurs +20 weeks after EoT.
- ^e Excluding MRIs, which have a visit window of -14 to -7 days.

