- ^k For patients who are already enrolled in this study who previously had an MRI before they transitioned to the new dosing regimen, the scheduled post-inclusion visit MRI should be calculated from the date of the inclusion visit. As the 32-week time point for MRI collection have been reached for patients from Study BN40697 prior to approval of Study BN40955 Protocol v4.0, these patients will have their Week 48 MRI collected then follow the 32-weekly schedule thereafter. For example: MRI will be collected at Week 49, followed by Week 65 and Week 97. Patients from Study BN40423 (enrolled prior to Study BN40423 protocol Versions 4) who have reached or have passed the 32-week visit schedule prior to Study BN40955 Protocol v4.0 approval at site will have unscheduled MRI at the next clinic visit once the site is active on Protocol v4.0 then continue with the 32-weekly schedule thereafter. For example: unscheduled MRI (next clinic visit following protocol being active at site), then followed by Week 65 and Week 97. Patients from Study BP40410 who have completed inclusion visit prior to Study BN40955 Protocol v4.0 or to Study BP40410 v4.0 approval at site will have unscheduled MRI at the next clinic visit once the site is active on Study BN40955 Protocol v4.0 then continue with the 32-weekly schedule thereafter. For example: unscheduled MRI (next clinic visit following protocol being active at site), then followed by Week 33, Week 65, and Week 97.

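### Between Week 49 and the end-of-treatment visit, the 32-weekly plasma biomarker and ADA draws fall 16 weeks out of phase with the 32-weekly MRI

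*Combined protocol and SAP*

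**What the plan says.** **Plasma.** In the schedules of activities (Appendices 1a and 1b), one frequency entry, "Q16W for 48 weeks and then Q32W thereafter", is printed at the plasma PK row. I read it as also covering the immunogenicity row and the row "Plasma samples for biomarkers", which show no treatment-period entry of their own. No list of plasma weeks is given. The PK and immunogenicity footnotes end plasma PK sampling with the pause and keep immunogenicity sampling going. Nothing withdraws the plasma biomarker row.

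**MRI.** Section 3.3.2.3 states: "All patients will undergo MRIs every 32 weeks to assess the effect of long-term treatment and LP on brain structure and function". Footnote k of Appendix 1a says, for patients already enrolled at the change of regimen, that "the scheduled post-inclusion visit MRI should be calculated from the date of the inclusion visit". Its example for patients from Study BP40410 is an unscheduled scan, "then followed by Week 33, Week 65, and Week 97". For patients from Study BN40697 it reads "MRI will be collected at Week 49, followed by Week 65 and Week 97". On timing, footnote e says: "Excluding MRIs, which have a visit window of -14 to -7 days".

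**End of treatment.** Both appendices mark structural MRI, plasma biomarkers and plasma immunogenicity at the end-of-treatment (EoT) visit. Plasma PK is not marked there.

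**CSF.** CSF is sampled at each dosing visit and, during the pause, every 16 weeks in all patients.

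**Use.** Section 2.5 lists as an exploratory endpoint: "Relationship between imaging biomarkers and efficacy, safety, PK, immunogenicity, or other biomarker endpoints". A companion endpoint relates plasma and CSF markers, such as tau and NfL, to the same set of outcomes.

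**The concern.** After Week 49, plasma and MRI have the same 32-week interval but start from points 16 weeks apart. Two series with the same period and a half-period offset do not meet at any scheduled treatment-period visit, however long the patient stays.

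Section 2.5 asks how plasma markers and immunogenicity relate to imaging. With this offset, an analysis of plasma NfL or tau against brain volume has to pair values taken about 16 weeks apart in a progressive disease. During the pause the two members of a pair also differ by about 16 weeks in time since the last dose. ADA is measured only in plasma, so a time-matched ADA and imaging comparison has no CSF substitute. Section 6.9 plans summaries by arm at each assessment time and gives no rule for pairing measurements from different visits.

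**Working it through.** This is calendar arithmetic, taking inclusion as Week 1 and about 6 years as 6 × 52 = 312 weeks, so to Week 313.

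1. **Reproduce the plan's own MRI weeks.** MRI week = 1 + 32k. For k = 1, 2, 3 this gives 33, 65, 97, which matches footnote k. Continuing to Week 313: 33, 65, 97, 129, 161, 193, 225, 257, 289, which is 9 post-baseline scans.

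2. **Derive the plasma weeks.** Sixteen-weekly for 48 weeks from Week 1: 1, 17, 33, 49. Then 49 + 32k: 81, 113, 145, 177, 209, 241, 273, 305. That is 12 draws.

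3. **Compare.** Up to Week 49 the shared visits are inclusion and Week 33. After Week 49 there are 8 scans (65 to 289) and 8 draws (81 to 305), with none shared. Nominal gaps: 81 − 65 = 16 and 97 − 81 = 16. To Week 97, 1 of 3 scheduled post-baseline scans has a same-visit draw; to Week 313, 1 of 9.

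4. **Allow for windows.** Visits may move by 1 week either way and the scan precedes the visit by 1 to 2 weeks, so the scan tied to Week 65 falls between Weeks 62 and 65 and the draw between Weeks 80 and 82. The draw is 80 − 65 = 15 to 82 − 62 = 20 weeks after that scan. The next scan falls between Weeks 94 and 97, so the draw is 94 − 82 = 12 to 97 − 80 = 17 weeks before it. The windows do not close the gap.

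5. **Exceptions.** Patients from BN40697 have a scan at Week 49, a plasma week, before returning to Weeks 65 and 97. Some patients from BN40423 and BP40410 have an unscheduled scan, which may or may not fall on a plasma week. Every patient who attends EoT has MRI, plasma biomarkers and ADA there.

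6. **CSF.** The lumbar puncture weeks during the pause are 1 + 16k. Every 1 + 32k is one of these, so every nominal MRI week has a CSF sample.

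7. **Other readings of the plasma entry.** Counting the 32-weekly phase from inclusion gives 1, 17, 33, 49, 65, 97, 129 and onward, in phase with MRI. Taking the 48 weeks as Weeks 1 to 48 and counting on from Week 33 gives 1, 17, 33, 65, 97 and onward, also in phase. The latter makes Week 33 the last 16-weekly draw, only 32 weeks after inclusion.

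**The case against.** The strongest reply is that little is lost and that the misalignment is not proven.

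- **The anchor is unstated.** Weeks 81, 113 and 145 appear nowhere. The only explicit anchor for a 32-weekly assessment is the inclusion visit, and on that anchor plasma and MRI coincide. Footnote k is itself loose: a strict 32-week count from the BN40697 scan at Week 49 would give 81 and 113, although its example gives 65 and 97. This stands as a caution. It does not remove the need to act, because the entry does not tell sites which grid to follow.
- **CSF covers most of the question.** The biomarker endpoint spans plasma and CSF. Section 3.3.2.1 ties CSF NfL to MRI atrophy, and Section 3.3.2.2 describes blood NfL as correlated with CSF NfL. NfL against brain volume can be studied at the same visit throughout, using CSF. This stands and narrows the point.
- **ADA status is a patient-level classification.** Section 6.8 derives it from all post-baseline samples, so relating that status to MRI needs no same-visit draw. This stands; only a time-matched ADA analysis is affected.
- **No planned analysis requires coincident visits.** The endpoint is exploratory, modelling is optional, and two longitudinal series at known times can be modelled jointly. This is fair, but such modelling must interpolate where a same-visit value could be had at almost no cost.

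A reader might infer that plasma and imaging are never measured together after Week 49, or that exposure–imaging pairs are still being lost. Neither is supported. EoT collects MRI, plasma biomarkers and ADA together, and plasma PK sampling stopped with the pause.

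**Conclusion.** The point holds in a limited form. On the natural reading of Appendices 1a and 1b, scheduled plasma biomarker and ADA draws do not coincide with MRI between Week 49 and EoT; they are nominally 16 weeks apart. For a patient followed for about six years without a catch-up scan, the scheduled post-baseline same-visit pairs are Week 33 and, if attended, EoT. Most patients may be followed for less time than this (the stated range is 6 months to about 6 years), so 8 unpaired scans is a maximum.

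The consequence is confined to the exploratory Section 2.5 relationships of plasma markers and time-matched ADA with imaging. It does not touch the safety objective, the CSF–imaging relationships or patient-level ADA status.

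The conclusion rests on three assumptions: the frequency entry applies to all three plasma rows; the 32-weekly plasma phase is counted from Week 49; and the inclusion-based MRI grid in footnote k of Appendix 1a applies generally, including to Appendix 1b. If the second is not what the sponsor intended, the defect is an unstated anchor rather than a misaligned schedule, and the same clarification cures it. This is a cheap improvement, not a flaw that threatens the study.

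**What to change.** For plasma biomarkers and immunogenicity in both appendices, change the entry to every 16 weeks for 64 weeks and every 32 weeks from then on, and print the anchor weeks: 1, 17, 33, 49, 65, then 97, 129, 161 and onward. Patients already on the Week 81 and 113 track make one 16-week step onto the MRI visits, for example from Week 81 to Week 97. Plasma PK needs no change while dosing is paused.

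All 8 MRI visits from Week 65 to Week 289 would then carry a plasma draw, at the clinic visit that follows the scan by 7 to 14 days. Weeks 65 and 97 are already lumbar puncture visits in both arms (Appendix 2b), the pattern continues beyond two years, and blood for hematology and chemistry is drawn at each clinic visit.

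Cost: schedule wording and lab-kit relabelling. The count to Week 313 is 12 draws either way (8 and 8 after Week 49), and the longest interval stays at 32 weeks. The downside is at most about one extra tube per patient, at the transition or for a patient who leaves soon after an MRI visit, for example between Weeks 65 and 80.
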